## List of Abbreviations

T2DM	Type 2 Diabetes Mellitus
SMBG	Self-monitoring blood glucose
HbA1c	Hemoglobin A1C / Glycated Haemoglobin
FBS	Fasting blood sugar
EMR	Electronic Medical Record

## Research Synopsis

Study title	Analogy As A Possible Effective Consultation Tool In Type II Diabetes Mellitus Patients on Insulin: A Retrospective Cohort Study
Objective	To determine the effectiveness of a novel consultation tool & method based on analogies in improving glycemic control among type 2 diabetes patients on insulin
Study Design	
This design will be a retrospective cohort study. We have clinical data of 107 T2DM patients registered in a newly established SMBG clinic in Klinik Kesihatan Senawang from 1 January 2023 to 1 July 2023. These clinic sessions are conducted once a week, and use a new structured consultation tool based on an analogy to explain and consult these patients. Patients are followed up every 2 months. Their HbA1c will be measured after 3 sessions of consultations (6 months). Patients who defaulted the follow up will be excluded.
 
We will prepare a medical record abstraction form and collect demographics and clinical data from the EMR. Demographic

[figure not shown]
	data included are patients' age and gender. Clinical data collected will be baseline HbA1c and FBS at first visit and third visit (after six months). Data will be analyzed to compare the following: (1) the percentage of patients achieving reduction of HbA1c and Fasting Blood Glucose (2) Average reduction of HbA1c and Fasting Blood Glucose
Study endpoints/outcomes	Reduction of HbA1c and Fasting Blood Glucose levels after six months, after a minimum of 3 SMBG clinic visits.
Study Population	All patients enrolled and registered at the SMBG clinic in Klinik Kesihatan Senawang from 1 January 2023 to 1 July 2023.
Inclusion/Exclusion Criteria	
Inclusion criteria
 
 
1. Established T2DM patients, already on insulin therapy regardless of the type of insulin or regime or duration of treatment
 
2. HbA1c at referral more than 8.5%
 
3. Already seen by diabetic educator or dietitian prior to referral
 
4. Completed a minimum of 3 follow-ups under the SMBG Clinic
 
5. Has repeated HbA1c recorded at 3 follow-ups
 
 
Exclusion Criteria
 
 
1. Pregnant, or found to be pregnant during follow up
 

Sample Size	106 Subjects (universal sampling)
Study Duration	15 March 2024 - 15 June 2024 (3 Months)

## 1. Background and Significance

- 1.1. Diabetes prevalence in Malaysia has been steadily increasing. According to data from the National Health and Morbidity Survey (NHMS), conducted by the Ministry of Health Malaysia, the rate of diabetes among adults aged 18 and above rose from 8.4% in 2011 to a concerning 13.4% in 2019. This significant increase in diabetes rates is a matter of great concern that requires immediate attention. As diabetes progresses over time, oral hypoglycemic agents (OHAs) may become less effective. Therefore, insulin therapy becomes necessary to maintain proper blood sugar control. The use of insulin therapy among Type 2 diabetes patients in Malaysia has been increasing to align with recent local and international diabetes guidelines.
- 1.2. Despite the growing use of insulin therapy, a significant number of patients fail to achieve long-term blood sugar control. Audits revealed that only a small percentage of patients on insulin therapy achieve the desired HbA1c level below 6.5%. Approximately 10-15% of patients successfully reach the recommended blood sugar targets. Research also indicates that insulin is often prescribed with less intensive regimens and insufficient dosage optimization.
- 1.3. Multiple obstacles hinder optimal blood sugar control, including poor medication adherence, hypoglycemia, inadequate insulin dosage adjustments, reluctance to escalate insulin regimens (especially those requiring more frequent injections), and the underutilization of mealtime and basal insulin within basal-bolus regimens. One of the most under-addressed reasons is the patient's insight and understanding of diabetes itself. Multiple studies have shown that knowledge has direct correlation with improved glycaemic control. Healthcare workers, particularly physicians are the ones who will provide information regarding diabetes. While there are local Clinical Practice Guidelines for T2DM, there is currently no standardized guide on how to actually communicate and disseminate this information.
- 1.4. In clinical practice, analogies are recognized as valuable tools for facilitating communication while enhancing doctor-patient interactions, particularly in elucidating complex medical concepts. It is widely used in oncology to communicate with patients about their current condition. When presented in vignette form, analogies have demonstrated a potential for increasing objective comprehension among patients. They offer a means for simplifying intricate medical concepts, thus improving patient comprehension and engagement, ultimately leading to better health outcomes. This represents a promising approach to enhancing doctor-patient communication in a very complex disease like T2DM. However, the effectiveness of analogies may vary depending on the complexity of the medical issue and the numeracy level of the individual, highlighting the importance of tailoring analogies to suit the needs and cultural context of the patient.
- 1.5. Hence, we developed a consultation tool based on the “Garbage, lorry, factory” analogy. In this analogy, the garbage represents glucose, the lorry represents insulin, and the factory represents the muscle. We tested this method through a

specialized clinic in Klinik Kesihatan Senawang, Negeri Sembilan from January 2023, where patients are referred to a 2-monthly consultation with primary care doctors. On the very first visit, patients are clerked to provide baseline background information. Then, they will be presented with the “Garbage and Lorry” analogy, assisted by a visual tool (Appendix 1), to explain the pathophysiology of T2DM. The presentation includes detailed lifestyle modification advice like diet, exercise, sleep. It ends with an explanation of the pharmacology of the common T2DM drugs and insulin, all guided by the same analogy. At the end of the consultation, patients would be given an insulin intensification protocol built based on Malaysia’s local guidelines that they would have to follow, and was given a follow up after 2 months, with a 4-point SMBG chart to be monitored a week before. The follow up would be reviewing the SMBG, and optimizing their insulin regime based on the blood glucose profile. Once their SMBG is optimized, their HbA1c is repeated. Figure 1 shows a flowchart of how the SMBG clinic runs.

- 1.6. If proven efficacious and viable, this innovative approach holds potential as a cost-effective strategy to enhance glycemic control among T2DM patients, potentially revolutionizing diabetes management in Malaysia.

[figure not shown]

(Figure 1 - SMBG Clinic KK Senawang Flow Chart)

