## **3. Methodology**

### **3.1 Study Design**

This design will be a retrospective cohort study. Clinical data of 107 T2DM patients enrolled in the SMBG clinic in Klinik Kesihatan Senawang from 1 January 2023 to 1 July 2023 (6 months) will be extracted from the electrical medical record (EMR). Patients who defaulted the follow up intervals will be excluded, as well as those without a repeated HbA1c. We will prepare a medical record abstraction form and collect demographics and clinical data. Demographic data included are patients' age and gender.

Clinical data collected will be baseline HbA1c and FBS at first visit and fourth visit (after six months). Data will be analyzed to compare the following: (1) the percentage of patients achieving reduction of HbA1c and FBS from baseline (2) Average reduction of HbA1c and FBS from baseline.

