### **3.3 Inclusion Criteria**

1. Established T2DM patients, already on insulin therapy regardless of the type of insulin or regime or duration of treatment
2. HbA1c at referral more than 8.5%
3. Already seen by diabetic educator or dietitian prior to referral
4. Completed a minimum of 3 follow-ups under the SMBG Clinic
5. Has HbA1c recorded at 6 months

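### Section 1.5 ties the repeat HbA1c to optimized SMBG, while the methods treat it as a six-month reading with no window or selection rule; HbA1c results may be mistimed and biased in either direction

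*Combined protocol and SAP*

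**What the plan says.** Section 1.5 (Background and Significance) says follow-up visits review SMBG and adjust insulin, and then: "Once their SMBG is optimized, their HbA1c is repeated". The readable text does not define optimized and gives no calendar time for this step.

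The other places anchor the same reading to time or to visit number:

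- Research Synopsis, Study Design: "Their HbA1c will be measured after 3 sessions of consultations (6 months", and data are taken at "baseline HbA1c and FBS at first visit and third visit (after six months".
- Research Synopsis, endpoints: "Reduction of HbA1c and Fasting Blood Glucose levels after six months, after a minimum of 3 SMBG clinic visits". This is a minimum number of visits, not a fixed one.
- Research Synopsis, inclusion criterion 5: "Has repeated HbA1c recorded at 3 follow-ups".
- Section 3.1: "Clinical data collected will be baseline HbA1c and FBS at first visit and fourth visit (after six months", and "Patients who defaulted the follow up intervals will be excluded, as well as those without a repeated HbA1c".
- Section 3.3, criterion 5: "Has HbA1c recorded at 6 months".

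Section 2 names HbA1c and FBS as primary outcomes. Section 3.9 plans a paired t-test or Wilcoxon signed-rank test, with no term for time of measurement and no method for missing readings.

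**The concern.** A reading ordered because glucose looks good is not a scheduled reading. If the clinic worked as section 1.5 describes, two things depend on response: when a patient's HbA1c was drawn, and whether it was drawn at all. The first affects what the average reduction and the percentage reduced mean. The second affects who is analysed, because a patient never judged optimized may have no repeat and would then be excluded under 3.1 and 3.3.

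There is no comparison group in which the same process would cancel out. The study is retrospective, so the draw dates are already fixed, and only the abstraction rule and the reporting can still deal with the problem. The trigger sentence concerns HbA1c; nothing comparable is said about FBS.

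**Working it through.** The plan has no power calculation or effect size to reproduce. The check is visit arithmetic followed by an illustration under assumed inputs.

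**1. Visit arithmetic.** Visits every 2 months (synopsis, section 1.5) fall at months 0, 2, 4 and 6. Month 6 is the fourth visit and the third visit is month 4, yet the synopsis equates the third visit with six months and 3.1 the fourth. The Figure 2 list gives a 6-week first review. Taking that as 1.5 months, the fourth visit falls at 1.5 + 2 + 2 = 5.5 months. So the nominal six-month reading is not one time point even without the SMBG trigger.

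**2. Good-spell effect, no true change.** Assumptions: visits at months 2, 4, 6 and 8; visit-to-visit HbA1c SD *s* = 0.5 to 0.8 points; correlation of SMBG with same-visit HbA1c *r* = 0.4 to 0.7; chance *p* = 0.5 to 0.3 of being judged optimized at each visit; HbA1c read at the first optimized visit. With φ the normal density at the *p*-quantile and *q* = (1 − *p*)⁴ the never-optimized share:

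- Never-optimized patients dropped: mean change = −*s r* φ/*p*.
 - Low end: 0.5 × 0.4 × 0.399/0.5 = 0.16 fall.
 - High end: 0.8 × 0.7 × 0.348/0.3 = 0.65 fall.
- Never-optimized patients kept and read at month 8: mean change = −*s r* [(1 − *q*)φ/*p* − *q*φ/(1 − *p*)].
 - Low end (*q* = 0.0625): 0.20 × (0.9375 × 0.798 − 0.0625 × 0.798) = 0.14 fall.
 - High end (*q* = 0.240): 0.56 × (0.760 × 1.159 − 0.240 × 0.497) = 0.43 fall.

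Timing alone, with nobody excluded, therefore gives a spurious fall of 0.14 to 0.43 points.

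**3. Adding a true fall that HbA1c reaches with a lag.** Let the expected change at month *t* be −*P*(1 − e^(−*t*/τ)), with assumed plateau *P* = 1 to 2 points and τ = 1.5 to 2.5 months. Assume too that the chance of being judged optimized is the same at every visit. Early readings miss part of the fall. Against a fixed month 6 the loss is *P*[Σ*w*ₜe^(−*t*/τ) − e^(−6/τ)], where *w*ₜ is the share read at month *t* (0.5, 0.25, 0.125, 0.125 for *p* = 0.5; 0.3, 0.21, 0.147, 0.343 for *p* = 0.3, never-optimized patients included at month 8).

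| *p* | *P* | τ | Loss from early reading | Good-spell gain (step 2, kept) | Net against fixed month 6 |
|---|---|---|---|---|---|
| 0.5 | 1 | 1.5 | 1 × (0.152 − 0.018) = 0.134 | 0.140 | 0.01 more favourable |
| 0.5 | 2 | 2.5 | 2 × (0.292 − 0.091) = 0.402 | 0.140 | 0.26 less favourable |
| 0.3 | 1 | 1.5 | 1 × (0.098 − 0.018) = 0.080 | 0.426 | 0.35 more favourable |
| 0.3 | 2 | 2.5 | 2 × (0.205 − 0.091) = 0.228 | 0.426 | 0.20 more favourable |

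A separate simulation had a lagged true fall, and its SMBG trigger carried no information about the noise in the HbA1c reading. It gave a triggered reading 0.12 to 0.28 points less favourable in every setting tried.

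**4. Selection.** Suppose only optimized patients have a repeat and the rest are excluded. The mean change then shifts towards benefit by ρ × SD × φ/*p*, where *p* is now the share ever optimized, ρ the correlation of SMBG status with HbA1c change, and SD that of the change (all assumed).

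- ρ = 0: no shift.
- ρ = 0.3, 70% optimized, SD 1.5 or 2.0: 0.3 × 1.5 × 0.497 = 0.22, or 0.3 × 2.0 × 0.497 = 0.30 points.
- ρ = 0.6, 50% optimized, SD 2.0: 0.6 × 2.0 × 0.798 = 0.96 points. With no true mean change, about 71% of those analysed would show a reduction instead of 50%.

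**The case against.** The best defence is that the operative sections already anchor the reading to the calendar. Section 3.3 requires "Has HbA1c recorded at 6 months" and 3.1 takes the value at the fourth visit, so on their wording a month-2 or month-4 value does not qualify. Section 1.5 is background. Its sentence may be a loose summary of the same process, and the Figure 1 flow chart, which is not shown in the text available, may state a timing rule. The sample size also equals the number enrolled, which fits a clinic where everyone was retested. If every patient had an HbA1c at six months, this mechanism adds no bias.

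Much of that stands and limits the claim. It does not remove the gap: a six-month criterion with no tolerance does not say which dated values qualify, the synopsis version of the criterion carries no date, and the plan does not say which reading to use if there are several.

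A reader might infer three stronger things that the documents do not support:

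- **That the reported reduction is inflated.** No HbA1c dates are given, and step 3 shows that the sign depends on how far the trigger picks out good spells and how far it catches patients before HbA1c has fallen.
- **That the timing effect is 0.16 to 0.65 points.** That range assumes no true change and drops never-optimized patients, so it mixes timing with selection.
- **That readings were spread over 8.6 to 14.6 months.** Those are the intervals from the last and first enrolment dates (1 July and 1 January 2023) to the 20 March 2024 start in 3.7. They bound how much record could exist, not when HbA1c was drawn.

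**Conclusion.** The conflict is real and unreconciled, and it concerns a primary outcome. If the section 1.5 flow generated the records, the HbA1c summaries may not be six-month results. They could be biased towards benefit, through good-spell testing or through exclusion of never-optimized patients without a repeat. They could also be biased against benefit, through testing early optimizers before HbA1c has fully fallen.

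Under the assumptions stated, timing alone runs from about 0.26 points less favourable to about 0.4 points more favourable than a fixed month-6 reading. Exclusion could add anything from nothing to nearly 1 point at the extreme setting. These figures show direction and range only, since every input to them is assumed. Confidence is high that the rule is unclear and medium at best on which way any bias runs. This should be fixed before abstraction. The finding does not extend to FBS.

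**What to change.** 1. Reconcile the synopsis, section 1.5, 3.1 and 3.3 on when HbA1c was in fact repeated, including the third-visit and fourth-visit labels.
2. In 3.1 and 3.3, define the primary follow-up HbA1c as the record value closest to 6 months after the first visit within a stated window (for example 5 to 7 months), chosen by date without regard to SMBG status.
3. Add two fields to the abstraction form: the HbA1c sample date, and whether SMBG had been declared optimized by then. Show the distribution of intervals from first visit to sample.
4. Report out-of-window values separately as a sensitivity analysis, not as six-month results.
5. Report how many of the 106 or 107 enrolled patients have no in-window HbA1c, and why. Add a sensitivity analysis that includes them, for example assuming no change. If *m* of *N* have no reading, that multiplies the observed mean change by (*N* − *m*)/*N*.

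Step 5 is needed because a date window alone leaves the selection in place: a value inside the window may still exist only because the patient responded.

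The cost is two fields, a wording change and one extra table. The price in results is a smaller primary n and possibly a less favourable estimate. If all readings prove to lie near six months and none is missing, the same fields will show that the concern does not apply.

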**First visit to SMBG clerking and consultation contents:**

1. Building Rapport
2. Social History
3. Co-morbidities History
4. The Diabetes History
5. The Diet History
6. The Activities & Exercise History
7. The Insulin History
8. The Blood Glucose Monitoring History
9. Summarizing
10. Improving Insight With Analogies
  - Presentation of the garbage & lorry analogy using a visual tool
11. Insulin Intensification
  - Education regarding how to titrate insulin based on the protocols
12. Given appointment in 6 weeks to review

(Figure 2 - SMBG Clerking and consultation content)

(Figure 3 - SMBG Clinic KK Senawang Insulin Intensification Protocol)

## **2. Objective**

To determine the effectiveness of a novel consultation tool based on analogies in improving glycemic control among type 2 diabetes patients on insulin with HbA1c and FBS as primary outcomes.

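### The objective is the effectiveness of the analogy tool, but an uncontrolled before-after comparison of a clinic package that also intensifies insulin cannot identify the tool's effect

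*Combined protocol and SAP*

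**What the plan says.** The sole objective (section 2) is "To determine the effectiveness of a novel consultation tool based on analogies in improving glycemic control among type 2 diabetes patients on insulin". Two primary outcomes are named there, HbA1c and FBS. The Research Synopsis has a slightly wider form: "novel consultation tool & method based on analogies in improving glycemic control".

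Section 1.5 describes what the clinic delivers. The analogy presentation covers pathophysiology, lifestyle advice and how the drugs work. At the end of the same consultation "patients would be given an insulin intensification protocol", and a 4-point SMBG chart is to be completed before the next visit. Follow-up consists of SMBG review and "optimizing their insulin regime based on the blood glucose profile". The first-visit content list has the analogy as item 10 and insulin intensification as a separate item 11: "Education regarding how to titrate insulin based on the protocols".

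Section 3.1 describes one clinic cohort with change from own baseline: "Clinical data collected will be baseline HbA1c and FBS at first visit" and again at about six months. Age and gender are the only other variables listed. Section 3.3 requires "HbA1c at referral more than 8.5"%. Section 3.9 plans a paired t-test or a Wilcoxon signed-rank test at P<0.05.

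Section 1.6 looks ahead to the result: "If proven efficacious and viable, this innovative approach holds potential as a cost-effective strategy to enhance glycemic control among T2DM patients".

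**The concern.** Effectiveness of a tool is a causal question: what would HbA1c have been without it? The plan contains nothing that stands in for that. Insulin intensification is itself meant to lower glucose, and it starts at the same visit as the analogy. A fall in HbA1c would therefore be expected even if the analogy did nothing.

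As the objective is worded, a significant paired test would naturally be read as evidence that the tool works, and section 1.6 builds on that reading. The study would then report an answer to a question that its data do not address.

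**Working it through.** **1. What differs between the two measurements.** The documents give no figure to reproduce here; 106 is a count of enrolled patients (section 3.6), not a calculated sample size. The check is to list what changes between baseline and six months, and to look for anything in the plan that separates the items.

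| Source of change | Where | Separated from the tool by |
|---|---|---|
| Analogy presentation | 1.5; list item 10 | (this is the target) |
| Insulin intensification protocol and titration teaching | 1.5; list item 11 | nothing |
| SMBG charting and review | 1.5 | nothing |
| Insulin adjustment at follow-up | 1.5 | nothing |
| Regression to the mean after selection on HbA1c | 3.3 | nothing |

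No control group, historical comparator, pre-referral trend or regression model is described. Insulin regimen and dose are not on the abstraction list, so the report could not even describe how much insulin changed. The mean paired difference is the sum of all these rows. A larger sample estimates that sum more precisely but does not split it.

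**2. How small a change is enough for significance.** With n=106 and two-sided alpha 0.05 (section 3.9 does not state sidedness), the mean change detectable at 80% power is (1.960 + 0.842)/√106 = 0.27 SD of the change. A modest fall from any cause would suffice.

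**3. Illustration of one non-tool component: regression to the mean in HbA1c.**

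From the documents: cut-off 8.5% (3.3), n=106 (3.6; the analysed number can only be smaller once defaulters are excluded), alpha 0.05 (3.9).

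Assumed, not in the documents: bivariate normal HbA1c; mean μ before selection 8.5 to 9.5%; SD σ 1.5 to 2.0; six-month within-person correlation r 0.6 to 0.8; baseline equal to the referral value; no effect of any care.

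Formulas:
- a = (8.5 − μ)/σ, and λ = φ(a)/(1 − Φ(a))
- Expected fall = σλ(1 − r)
- Variance of change = (1 − r)²σ²(1 + aλ − λ²) + σ²(1 − r²)
- Rejection rate from the noncentral t with 105 df and noncentrality √106 × fall/SD of change
- Share of patients with a reduction, by simulation

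| μ, σ, r | λ | Fall (points) | SD of change | Rejection | Share reduced |
|---|---|---|---|---|---|
| 8.5, 2.0, 0.6 | 0.798 | 2.0×0.798×0.4 = 0.64 | 1.67 | 97% | 65% |
| 9.0, 1.5, 0.7 | 0.599 | 1.5×0.599×0.3 = 0.27 | 1.11 | 70% | 59% |
| 9.5, 1.5, 0.8 | 0.427 | 1.5×0.427×0.2 = 0.13 | 0.93 | 29% | 55% |

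The first and last rows bound the assumed grid. Raising r to 0.9 lowers the floor to a fall of 0.06 points and 17% rejection.

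**4. If baseline is a fresh first-visit value.** The expected fall becomes σλ(r₁ − r₂), where r₁ and r₂ are the correlations of the referral value with the first-visit and six-month values. It is nil when they are equal and always smaller than in step 3.

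**The case against.** The strongest objection is to the numbers. The synopsis and section 3.1 both place baseline HbA1c at the first visit, while the 8.5% cut-off applies at referral. On a plain reading these are different measurements, and regression to the mean is then small or nil. This stands as a limit on step 3. Section 3.1 does not say that a fresh sample was taken, so neither reading can be excluded. The figures also cover HbA1c only (no criterion selects on FBS), rest on assumed inputs, and do not size the confounding by insulin intensification, for which the documents give no data. They are an illustration, and the main point does not depend on them.

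A second objection is that the synopsis wording, which adds a method to the tool, could mean the whole structured consultation. That is a fair reading of the synopsis. Section 2 drops the addition, however, and the content list separates the analogy from insulin intensification. If the package is meant, the objective should say so.

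Third, every patient was already on insulin and had already seen an educator or dietitian (3.3). This weakens starting insulin and first-time education as rival explanations. It leaves intensification and SMBG review untouched.

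Fourth, the title calls the tool only possibly effective, and section 1.6 is conditional. Neither restricts what may be concluded from a significant result.

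Finally, an uncontrolled review of routine care is legitimate and its before-after estimates remain reportable. That is agreed; the fault lies in the claim attached to them.

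**Conclusion.** The concern holds and must be fixed. As written, the only objective cannot be answered by the planned data at any sample size, because patients receive the analogy together with insulin intensification and SMBG and nobody serves as a comparator. This conclusion follows from the documents and needs no assumed figure.

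The size of the non-tool change cannot be derived from the documents. Under the stated assumptions, regression to the mean alone could produce anything from a trivial fall to an almost certainly significant one. That range shows why a P value below 0.05 would not be evidence for the tool.

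**What to change.** **Core change (wording only).** In section 2 and the synopsis, restate the objective and the permitted conclusion as the change in HbA1c and FBS after enrolment in the SMBG clinic package: analogy consultation, insulin intensification and SMBG together. State that no effect will be attributed to the analogy alone, and bring section 1.6 into line. The cost is a weaker claim about the tool.

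**Baseline.** In section 3.1, say whether baseline HbA1c is the referral value used for the 8.5% criterion or a separate first-visit measurement, and name regression to the mean as a limitation.

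**Secondary and conditional.** Where the EMR holds them, abstract insulin regimen, total daily dose and other glucose-lowering drugs at first visit and at six months. Report them descriptively beside the HbA1c change, stating that they do not isolate the tool's effect. This adds a few items per record. The documents do not show whether six-month dose is retrievable or whether the extraction covered by the consent waiver includes it. Do not compare patients with and without a dose increase: dose change may be one route by which the tool works, and it is confounded by indication.
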